**Study Completion** 

|   |          |                  | Screening period |                 |     | ent l                    |    | d for | Induction | on and | Mainter                  | nance p | hases fo | or LGG |    | Post Treatm  | ent Period   |                                      |
|---|----------|------------------|------------------|-----------------|-----|--------------------------|----|-------|-----------|--------|--------------------------|---------|----------|--------|----|--|--|--------------------------------------|
|   | Category | Protocol Section | Screening        | As
(W
± 2 | eek | smer
s 1 to
/ visi | 5) |       | (Week     | s 8 to | k Asses
56)
window | sments  |          |        |    | End of treatment
(EoT)
Within 30 days
after last dose | Post Treatment Follow up Every 16 weeks ±14 day visit window | Survival follow up
Every 3 months |
| Week  |          |                  | -28 to -1        | 1               | 2   | 3                        | 4  | 5     | 8         | 16     | 24                       | 32      | 40       | 48     | 56 |  |  |                                      |
| End of Phase
Disposition                                       | D        | 7.1.4            | X                |                 |     |                          |    |       |           |        |                          |         |          |        |    | Х  | Х  |                                      |
| Antineoplastic therapies since discontinuation of study treatment | D        | 7.1.6.1          |                  |                 |     |                          |    |       |           |        |                          |         |          |        |    | Х  | Х  | Х                                    |
| Survival Follow-up  | D        | 7.1.6.2          |                  |                 |     |                          |    |       |           |        |                          |         |          |        |    |  |  | Х                                    |

# 7.1.1 Molecular pre-screening

There is no molecular pre-screening for this study.

# 7.1.2 Screening

Written informed consent/assent must be obtained prior to any screening procedures. The window for screening each patient will be up to 28 days before the first dose, including a serum pregnancy test for women of childbearing potential. A urine pregnancy test must conducted and confirmed negative on Day 1 before dosing. Adverse events will also be recorded at this visit. Screening assessments to confirm eligibility should be performed as per the schedule of assessments (Table 7-1, Table 7-2, Table 7-3).

Local *BRAF* V600 mutation result may be used to qualify patients for enrollment, as part of the study inclusion criteria listed in Section 5.2. The CRF page for method of local *BRAF* V600 mutation testing, including the methodology used for local assessment, must be completed for patients whose tumor sample was tested by a local institutional assay. *BRAF* V600 mutation result must be locally documented prior to Day 1 (HGG cohort) or randomization (LGG cohort). The *BRAF* V600 mutation status will be assessed using a validated tissue-based test. Molecular-based *BRAF* V600 testing should be used where available and is strongly preferred over non-molecular methods, e.g. immunohistochemistry. Liquid biopsy-based *BRAF* V600 results cannot be used to enroll patients. *BRAF* V600 mutation results will be subjected to retrospective central confirmation by a Novartis designated laboratory. For the retrospective central confirmation all subjects will be required to provide a tumor tissue sample at screening prior to study treatment, as either a tumor block or a minimum of 20 FFPE slides (see Table 7-8). Central confirmation of *BRAF* V600 mutation status is not required for enrollment, if local test results are positive for *BRAF* V600 mutation. Patients will not be excluded if central testing is later found to be discordant or uninformative (e.g. inadequate sample).

For patients who do not have a *BRAF* V600 mutation result documented locally, a tumor sample must be submitted for central testing of *BRAF* mutation status during screening. The minimum requirements for this sample are listed in Table 7-8.

A patient who has a laboratory test result(s) that does not satisfy the entrance criteria may have the test(s) repeated within the screening window (within 28 days from the first dose). In this case, the patient will not be required to sign another ICF, and the original patient ID number assigned will be used. In the event that the laboratory test(s) cannot be performed within 28 days of the original screening visit, or the re-test(s) do not meet the entrance criteria, or eligibility criteria have changed and are not met anymore, the patient is considered a screen failure.

A new ICF/assent will need to be signed if the investigator chooses to re-screen the patient after a patient has screen failed, however the patient ID number will remain the same. All required screening activities must be performed when the patient is re-screened for participation in the study.

# 7.1.2.1 Eligibility screening

Following registering in the IRT for screening, patient eligibility will be checked once all screening procedures are completed. The key eligibility check will be embedded in the IRT system. Please refer and comply with detailed guidelines in the IRT manual.

### 7.1.2.2 Information to be collected on screening failures

Patient who signed an Informed Consent Form but failed to be started on treatment for any reason will be considered a screen failure.

The demographic information, informed consent/assent, Inclusion/Exclusion and Screening Phase Disposition pages must be completed for screen failure patients. No other data will be entered into the clinical database for patients who are screen failures, unless the patient experienced a Serious Adverse Event during the Screening Phase (see Section 8 for SAE reporting details).

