#### Data analysis to address secondary objectives:

ORR per investigator assessment for HGG cohort and LGG cohort will also be analyzed.

TTR, DOR, CBR and PFS will be analyzed as per investigator and independent assessment. Confirmation of response is required for all response endpoints, as per RANO.

DOR, PFS and OS will be described using Kaplan-Meier methods and appropriate summary statistics.

**Efficacy:** The efficacy analysis will be performed on all patients who receive at least one dose of study treatment. Sensitivity analysis on the primary and secondary efficacy endpoints will be performed on the evaluable set of patients.

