Patients who discontinue study treatment and efficacy follow-up, and have completed the post-treatment skin examination will enter the post treatment follow-up period during which survival will be collected every 3 months. During the survival follow-up, subsequent anti-neoplastic therapies initiated after study treatment discontinuation and response to those treatments will be collected.

All patients will be followed for survival for at least 2 years after the last patient first study treatment (except if consent is withdrawn, death, or patient is lost to follow-up or study discontinuation).

No formal interim analysis is planned for the LGG cohort.

The primary analysis will be conducted based on all treated patients when all patients have either completed at least 32 weeks of treatment or have discontinued earlier.

[figure not shown]

Figure 4-2 Study Design for LGG Cohort

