## 6.5 Patient numbering, treatment assignment or randomization

#### 6.5.1 Patient numbering

Each patient is identified in the study by a Subject Number (Subject No.), that is assigned when the patient is first enrolled for screening and is retained as the primary identifier for the patient throughout his/her entire participation in the trial. The Subject No. consists of the Center Number (Center No.) (as assigned by Novartis to the investigative site) with a sequential patient number suffixed to it, so that each patient is numbered uniquely across the entire database. Upon signing the informed consent form, the patient is assigned to the next sequential Subject No. available to the investigator through the Oracle Clinical RDC interface.

The investigator or designated staff will contact the IRT and provide the requested identifying information for the patient to register them into the IRT. Once assigned, the Subject No. must not be reused for any other patient and the Subject No. for that individual must not be changed, even if the patient is re-screened. If the patient fails to start treatment or is not randomized (LGG cohort) for any reason, the reason will be entered into the Screening Disposition page.

IRT must be notified within 2 days that the patient did not receive study drug or was not randomized (for LGG cohort).

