# 7.1.4.1 Replacement policy

Patients will not be replaced on study.

However, if a patient is considered as non-evaluable for the per-protocol set (PPS), enrollment of a new patient will be considered if there is less than the required number of evaluable patients.

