# 10.1 Analysis sets

### 10.1.1 Full Analysis Set

The Full Analysis Set (FAS) for the HGG cohort will include all patients to whom study treatment has been assigned and who receive at least one dose of study treatment.

For the LGG cohort the FAS comprises all patients to whom study treatment has been assigned by randomization regardless of whether or not treatment was administered. According to the intent to treat principle, patients will be analyzed according to the treatment they have been assigned to during the randomization procedure.

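### The screen-failure rule in Section 7.1.2.2 stops data entry for randomised LGG patients who never start treatment, which contradicts the all-randomised FAS used for the ORR, PFS and OS tests

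*Protocol*

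**What the plan says.** **Screen failures.** Section 7.1.2.2 applies to both cohorts: "Patient who signed an Informed Consent Form but failed to be started on treatment for any reason will be considered a screen failure". Only the demographic, consent, inclusion/exclusion and screening disposition pages are completed. Beyond these, "No other data will be entered into the clinical database for patients who are screen failures", with an exception only for a serious adverse event in screening. Section 6.5.1 handles non-starters in the same way and names the LGG cohort: "If the patient fails to start treatment or is not randomized (LGG cohort) for any reason, the reason will be entered", on the Screening Disposition page. Tables 7-1 and 7-3 place IRT randomisation in the screening column, so a patient can be randomised and then never dosed.

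**Analysis population.** For the LGG cohort, Section 10.1.1 says "the FAS comprises all patients to whom study treatment has been assigned by randomization regardless of whether or not treatment was administered", analysed as assigned. Section 10.4.2 puts the primary ORR test on the FAS. Section 10.5 does the same for secondary efficacy and tests PFS, then OS, in sequence after ORR. Both times run from randomisation.

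**Conflicting wording.** The protocol summary, under the secondary objectives and with no cohort named, says "The efficacy analysis will be performed on all patients who receive at least one dose of study treatment". Section 4.1, in the LGG text, says "The primary analysis will be conducted based on all treated patients" and goes on to give the 32-week timing.

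**The concern.** The FAS definition and the data-collection rule give opposite instructions for the same patients. A site that follows Section 7.1.2.2 would enter no tumour assessment, new therapy or survival status for a randomised LGG patient who was never dosed. The analysis plan needs that patient in the denominator and in the time-to-event comparisons. An SAP can choose a population, but it cannot restore data that the protocol told sites not to enter.

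The cohort is open label. Control is a 12-week induction followed by eight 6-week cycles of intravenous chemotherapy, 12 + 8 × 6 = 60 weeks, and the experimental treatment is oral. Unequal non-start between arms is therefore plausible. If it occurred, untreated patients would be scored as non-responders without being observed, and would contribute no follow-up to PFS or OS. Those two comparisons would then not be fully as randomised.

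**Working it through.** **1. Where the data go.** For a randomised, never-treated LGG patient:

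| Item | Consequence | Source |
|---|---|---|
| Arm and denominator | Known, since IRT data are transferred to the sponsor | 9.3, 9.4 |
| Best overall response | Missing, counted as failure | 10.4.3 |
| Progression, new therapy | Not entered | 7.1.2.2 |
| Survival | Contradictory: 4.1 follows all patients for survival, 7.1.2.2 bars entry | 4.1, 7.1.2.2 |

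Post-treatment follow-up (Sections 4.1.3, 7.1.4 and 7.1.6.1) is written for patients who discontinue or complete treatment. It does not mention those who never start.

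**2. The planned figure.** Section 10.8.2 gives 102 randomised, 2:1 (68:34), ORR 50% against 20%, one-sided 2.5%, power 80%.
- Pooled rate: (34 × 0.20 + 68 × 0.50)/102 = 0.40.
- Standard error under the null: √[0.40 × 0.60 × (1/34 + 1/68)] = 0.1029.
- Standard error under the alternative: √[0.16/34 + 0.25/68] = 0.0916.
- Continuity correction: (1/34 + 1/68)/2 = 0.0221.
- Power: Φ[(0.30 − 0.0221 − 1.96 × 0.1029)/0.0916] = Φ(0.83) = 79.8%.

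Exact enumeration of the Mantel-Haenszel test gives 79.9% with the correction and 86.3% without. The stated power therefore corresponds to the corrected calculation on all 102 randomised, with no allowance for non-starters. Section 10.4.2 does not say whether the test itself is corrected, so both versions are shown below.

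**3. Rejection under equal ORR (assumed non-start).** Let k of 34 controls and j of 68 experimental patients not start and be scored as failures. Responders are binomial among the remaining 34 − k and 68 − j, the denominators stay at 34 and 68, and the statistic is z = (x_t − 68m/102 − c)/√v. Here x_t is the number of experimental-arm responders, m is total responders, v = 34 × 68 × m(102 − m)/(102² × 101), and c is 0 or 0.5. Reject if z ≥ 1.96.

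| k, j | ORR 20%, uncorrected | ORR 20%, corrected | ORR 35%, uncorrected | ORR 35%, corrected |
|---|---|---|---|---|
| 0, 0 | 2.1% | 0.9% | 2.4% | 1.4% |
| 3, 0 | 3.2% | 1.5% | 4.5% | 2.6% |
| 5, 0 | 4.2% | 2.0% | 6.7% | 4.0% |
| 3, 6 (proportional) | 1.9% | 0.8% | 2.2% | 1.2% |

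If the control non-starters are instead dropped at random, uncorrected rejection stays at about 2.0% to 2.4%, but the analysis is no longer as randomised.

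**4. Does the choice of population matter?** With ORR 20% against 50% among starters and the corrected test, 4 control non-starters give power of 87.3% on the FAS and 76.1% on treated patients. With 3 control and 6 experimental non-starters the figures are 73.7% and 76.2%. The two readings part as soon as anyone fails to start.

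**The case against.** The best reply is that the FAS is not in doubt. Section 10.1.1 is explicit, the protocol summary and Sections 4.1 and 10.4.2 all put the primary analysis on it, and Section 10.4.3 says how patients without a valid assessment are scored. A reader might infer that the primary ORR test cannot be run on all randomised patients. The documents do not support that, because arm, denominator and scoring rule are all available.

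The treated-patient wording is also weaker than it looks. The Section 4.1 sentence is largely about timing; Section 10 uses similar words for timing only, and Section 10.7.2 gives the LGG timing for all patients. The summary sentence fits the HGG FAS, which is a treated set. Both need aligning, but neither overrides Section 10.

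The rejection rates are conditional. They require non-start in the control arm only, and non-starters who would otherwise have responded at the common rate. Much of the effect is non-responder scoring, which better data collection would not remove. Section 10.4.4 lists an ORR that counts responses irrespective of new therapy as a sensitivity analysis, which suggests that the primary ORR does not count them. A control patient who declined chemotherapy and took something else could then remain a failure even with full follow-up.

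What stands is the data rule. Nothing in the protocol exempts a randomised patient from Section 7.1.2.2, and Section 6.5.1 repeats its routing.

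**Conclusion.** The point holds as a contradiction between a data-collection rule and the randomised analysis set. The main loss is in PFS and OS, which run from randomisation and are formally tested after ORR. Progression data would be absent for untreated members of the FAS, and survival data would depend on which of two conflicting statements a site followed. A reader might infer that PFS and OS are lost entirely for these patients. That goes too far, because Section 4.1 says all patients are followed for survival.

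For ORR the size is not known. With 3 to 5 of 34 control non-starters and none in the other arm, one-sided rejection under equal ORR of 20% to 35% is 3.2% to 6.7% uncorrected or 1.5% to 4.0% corrected. With proportional non-start it does not exceed 2.2%. The number and arm of non-starters are assumptions. It is also tempting to conclude that refusal will fall mainly on the control arm; the protocol gives no data on this, and crossover after centrally confirmed progression gives controls a reason to stay.

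**What to change.** 1. In Sections 7.1.2.2 and 6.5.1, define screen failure for the LGG cohort as not randomised.
2. State that every randomised LGG patient stays in the database, with tumour assessments, new anti-cancer therapy and survival collected on the existing schedule whether or not treated, subject to consent.
3. In the protocol summary and Section 4.1, replace the treated-patient wording by the FAS: all randomised for LGG, all treated for HGG.

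The cost is protocol wording, a case report form instruction and follow-up of a few untreated patients. The sample size does not change. At Amendment 5, 44 of about 102 LGG patients had been randomised, so roughly 58 would be covered from the start.

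As a separate tidy-up, Section 7.1.4.1 says that "if a patient is considered as non-evaluable for the per-protocol set (PPS), enrollment of a new patient will be considered", while Section 10.1.3 gives the per-protocol set as not applicable. Remove or reconcile that sentence.

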# 7.1.2.3 Patient demographics and other baseline characteristics

The data that will be collected on patient characteristics at screening includes:

- Demography (Year of birth, calculated age, sex, childbearing status, race, ethnicity)
- Histologically confirmed diagnosis of High Grade Glioma (Grade III or IV glioma) or Low Grade Glioma (Grade I or II glioma), as defined by WHO histological classification system, 2016.
- Medical history (e.g., important medical, surgical, and allergic conditions from the patient's medical history which could have an impact on the patient's evaluation) / current medical conditions (e.g., all relevant current medical conditions which are present at the time of signing informed consent/assent). Frequency of seizures prior to the first day of dosing should be assessed and recorded on the Medical History eCRF. For LGG patients, the indication to treatment must be reported which may include clinical and/or neurological symptoms. Ongoing medical conditions, symptoms and disease which are recorded on the Medical History eCRF should include the toxicity grade.
- All prior antineoplastic therapies including surgical interventions and chemo-, biologic-, immunologic- and radiation-therapies provided as treatment for cancer prior to the administration of study drug.
- All medications and significant non-drug therapies taken within 30 days before the first
  dose is administered. They must be recorded on the Prior and Concomitant medication or
  Surgical and medical procedures eCRF page and updated on a continual basis if there are
  any new changes to the medications.

Furthermore the following assessments will be performed:

- Central confirmation of HGG histopathology (HGG cohort only) and *BRAF* V600 mutation (HGG and LGG cohorts) (Tumor tissue required)
- Radiological assessments (e.g. MRI) to confirm measurable disease per RANO response criteria (locally determined and central confirmation required before enrollment)

- Vital signs
- Height, weight
- Physical examination

- Performance status (Karnofsky/Lansky)
- Laboratory evaluations (hematology, chemistry, urinalysis)
- Pregnancy testing (for menstruating females and women of childbearing potential)
- Hepatitis testing (for patients with a history of hepatitis)
- ECG
- ECHO
- Ophthalmology exam
- Dermatological exam

# 7.1.3 Treatment period

Following completion of screening procedures and verifying patient eligibility, patients will complete registration in IRT and start study treatment. HGG patients and LGG patients randomized to dabrafenib with trametinib will have weekly visits for the first 5 weeks, followed by visits every 8 weeks until the end of the first year; subsequent visits will occur every 16 weeks. LGG patients randomized to chemotherapy will follow the same visit schedule for protocol assessments, but will be required to return to the clinical site for additional chemotherapy dosing visits per Section 6.1.2.

For details of assessments, refer to Table 7-1, Table 7-2 for LGG crossover patients and Table 7-3.

Concomitant medication, adverse events and SAE monitoring will be continuous throughout the trial

Patients will be treated with study treatment until disease progression, unacceptable toxicity, death or discontinuation from the study treatment due to any other reason.

# 7.1.3.1 Treatment after Progression of Disease

Patients will be permitted to continue dabrafenib with trametinib beyond investigator-assessed, RANO-defined PD, as long as they meet the following criteria:

- Investigator assessed clear evidence of clinical benefit
- Tolerance of study drug
- Continuation of study treatment is in the best interest of the patient as determined by the Investigator
- Patient/legal guardian is willing to continue on the study and signed ICF for treatment beyond progression

If the Investigator determines that all above criteria are met, the patient may continue study treatment and follow all study related procedures, including tumor assessments, as scheduled in Table 7-1, Table 7-2 for LGG crossover patients and Table 7-3. After each tumor assessment,

the investigator must confirm if the patient is still benefitting from study treatment, and document this in the patient's chart and the appropriate CRF pages.

## 7.1.4 Discontinuation of study treatment

Patients may voluntarily discontinue from the study for any reason at any time. If a patient decides to discontinue from the investigational treatment, the investigator should make a reasonable effort (e.g. telephone, e-mail, letter) to understand the primary reason for this decision and record this information in the patient's chart and on the appropriate CRF pages. They may be considered withdrawn if they state an intention to withdraw, fail to return for visits, or become lost to follow-up for any other reason.

For patients who discontinue treatment for reasons other than documented disease progression, death, lost to follow-up, or withdrawal of consent/assent, tumor assessments must continue to be performed every 16 weeks until documented disease progression, death, lost to follow-up, or withdrawal of consent/assent.

Patients must be discontinued under the following circumstances:

- Pregnancy
- Study Terminated by Sponsor
- Patient/guardian decision
- Physician decision (investigator may discontinue study treatment for a given patient if, he/she believes that continuation would be detrimental to the patient's well-being)
- Any other protocol deviation that results in a significant risk to the patient's safety

Patients who discontinue study treatment should NOT be considered withdrawn from the study. They should return for the assessments indicated in Section 7.2.1. If they fail to return for these assessments for unknown reasons, every effort (e.g. telephone, email, letter) should be made to contact them as specified in Section 7.1.7. The investigator must also contact the IRT to register the patient's discontinuation from the study.

In some circumstances patients may be allowed to continue to receive study treatment beyond disease progression as per RANO criteria (Section 7.1.3.1). These patients will continue assessments as outlined in Table 7-1, Table 7-2 for LGG crossover patients or Table 7-3, and will complete the End of Treatment visit only after permanent discontinuation of study treatment.

